6.2.2.2 Primary analyses of secondary efficacy variables

The primary analysis of secondary efficacy variables will be performed in PPS. The secondary efficacy variables will be analyzed using similar statistical methods as for the primary efficacy variable, i.e. the MCP-Mod method with the same standardized candidate dose-response shapes and corresponding coefficients as for the primary variable. The missing values of post-baseline at week 20 will be imputed by WOV if the baseline values are not missing and the subjects have CV death or HF hospitalization, otherwise remain missing.

For variables related to KCCQ and activity, the worst observation value (WOV) would be imputed as follows:

- 1) First, the worst change from baseline value by each treatment group will be calculated. If any of them is positive, the value would be set to 0.
- 2) Secondly the median of the worst changes from baseline value among all treatment groups would be calculated. The change from baseline value for all the missing data will be imputed with a multiplier 1.0 of this median value.
- 3) The WOV (i.e. imputed post-baseline value at week 20) will be calculated accordingly as baseline value + imputed change from baseline. If this imputed WOV is less than 0 (in case of either CV death or a hospitalization for HF preventing the measurement), then the WOV will be replaced with 0 and the imputed change from baseline will be modified to (- baseline value) accordingly.

For variables of biomarkers (log-transformed NT-proBNP and log-transformed hs-TNT), the worst observation value (WOV) would be imputed as follows:

- 1) First, the worst change from baseline value by each treatment group will be calculated. If any of them is negative, the value would be set to 0.

Statistical Analysis Plan

2) Secondly the median of the worst changes from baseline value among all treatment groups would be calculated. The change from baseline value for all the missing data will be imputed with a multiplier 1.0 of this median value.

In addition to analyses comparing population means in the different dose groups, the number of patients in whom the individual change from baseline value crossed clinically meaningful thresholds will be analyzed.

All other efficacy variables will be analyzed descriptively.

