Figure 6—1 shows the corresponding dose-response shapes. The model parameters were obtained through discussions with experts in the clinical team, taking prior beliefs and uncertainty into account.

Statistical Analysis Plan

Table 6—1: Dose-response shapes used in the candidate set

Model	Response as function of dose d
Linear	d
Sigmoidal E_{max} 1	$40.1 d^4 / (9^4 + d^4)$
Sigmoidal E_{max} 2	$45 d^3 / (20^3 + d^3)$
E_{max}	$41.25 d / (1.25 + d)$
Quadratic	$2.667 d - 0.044 d^2$

Figure 6—1: Dose-response shapes used in the candidate set

Based on the standardized versions of the models in the candidate set and the sample size allocation planned for this study, the optimum contrast coefficients for the 5 contrast tests on the dose-response shapes can be derived for the primary variable.

Analysis

Step 1: Detection of dose-response signal

For detecting an overall trend, or a dose-response signal, each of the $M=5$ dose-response shapes in the candidate set will be tested, using a single contrast test based on the updated version of contrast coefficients taking the actual sample sizes per treatment group into account.

For each model m , $m = 1, \dots, 5$, in the candidate set

the null hypothesis $H_{0m}: c_m \mu_m^0 = 0$

will be tested against

Statistical Analysis Plan

Protocol No.: < BAY 1067197/17582 >

Page: 20 of 38

the respective 1-sided alternative hypothesis $H_{1m}: c_m \mu_m^0 > 0$,

where $\mu_m^0 = (\mu_{m1}^0, \dots, \mu_{m6}^0)' = (f_m^0(d_1, \boldsymbol{\theta}_m^0), \dots, f_m^0(d_6, \boldsymbol{\theta}_m^0))'$ and

f^0 is the standardized version of the dose-response model $f(d, \boldsymbol{\theta}) = \theta_0 + \theta_1 f^0(d, \boldsymbol{\theta}^0)$. In this parameterization, θ_0 is a location parameter and θ_1 is a scale parameter such that only $\boldsymbol{\theta}^0$ determines the shape of the model function.

The contrast coefficients $c_{m1} \dots c_{m6}$ for the m -th model are chosen such that they maximize the power to detect the underlying model. These optimal contrast coefficients depend only on the parameters in the standardized model function $\boldsymbol{\theta}^0$, which determine the model shape (1) and the actual group sample sizes (which is known after unblinding of the study). The i th member of the optimal contrast vector $\mathbf{c}_{opt,m}$ for testing the shape model m is proportional to

$$n_i(\mu_{mi}^0, \dots, \bar{\mu}), i = 1, \dots, 6,$$

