where $\bar{\mu} = N^{-1} \sum_{i=1}^6 \mu_{mi}^0 n_i$. In case of unequal sample sizes per treatment arm, $\mathbf{c}_{opt,m}$ cannot be expressed in closed form and numerical optimization techniques are required (1, 3). The $\mathbf{c}_{opt,m}$ is derived by fulfilling the condition $\sum_{i=1}^6 c_{mi}^2 = 1$.

The single contrast test for detecting the m -th model shape is defined by

$$T_m = \frac{\sum_{i=1}^6 c_{mi} \bar{Y}_i}{S \sqrt{\sum_{i=1}^6 c_{mi}^2 / n_i}}, m = 1, \dots, 5, \quad \text{where } S^2 = \frac{\sum_{i=1}^6 \sum_{j=1}^{n_i} (Y_{ij} - \bar{Y}_i)^2}{N-6}.$$

Under the null hypothesis of no dose-response effect, i.e. $\mu_{d_1} = \dots = \mu_{d_6}$, the test statistic $T = (T_1, \dots, T_5)'$ follows a central multivariate t distribution with $N-6$ degrees of freedom and correlation matrix $R = (\vartheta_{ij})$, where $\vartheta_{ij} = \frac{\sum_{l=1}^6 c_{il} c_{jl} / n_l}{\sqrt{\sum_{l=1}^6 c_{il}^2 / n_l \sum_{l=1}^6 c_{jl}^2 / n_l}}$.

The final test statistic T_{max} is based on the maximum contrast test and a “proof-of-concept” dose-response relationship is detected if this maximum statistic T_{max} , and thus at least one single contrast test, is statistically significant, while controlling the familywise error rate at level α . If $q_{1-\alpha}$ denotes the multiplicity adjusted critical value, a dose-response signal is established if $T_{max} \geq q_{1-\alpha}$.

This analysis will be performed for the FAS and PPS populations, where the PPS analysis is the primary analysis.

If no candidate model is statistically significant, the procedure stops, indicating that a dose-response relationship cannot be established from the observed data.

Out of the statistically significant models in the candidate set a best model can be selected for the next step: modeling and estimation.

Step 2: Modeling and estimation of target doses

If a dose-response signal is established, the selected dose-response model(s) will be fitted to the observed data to estimate the model parameters.

The estimated dose-response model will be plotted against the doses including 90% confidence bands. Once the dose-response model has been successfully fitted to the data,

Statistical Analysis Plan

target dose(s) of interest are estimated. Given a clinically relevant effect Δ , a minimum effective dose (MED_{Δ}) associated with model $f(d, \theta)$ is defined as

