6.2.1.4.2 Sensitivity analysis of primary efficacy variable in FAS

Additional efficacy analyses in the FAS will include the following:

- Primary analyses of primary efficacy variable specified in Section 6.2.1.2 will be performed in FAS without any imputation.
- Generally, it will be assumed that missing observations for the respective efficacy variables are missing at random. This implies that the behavior of the post dropout observations can be predicted from the observed variables using appropriate imputation models. Likely exceptions to the missing at random assumption are observations which are missing due to a patient's CV death or HF hospitalization prior to the visit in Week 20. These observations can be assumed to be missing not at random (MNAR), i.e., that missingness depends both on observed and unobserved outcomes and that an explicit model for the patient's statistical behavior after drop-out (or death) is required. Therefore, an analysis based on a pattern mixture framework (5) with different imputation rules depending on the reason for missingness will be used using a multiple imputation model, followed by a modification of the imputed data applying penalties:
 1. First, multiple imputation will be applied to draw sets of completed data, using an appropriate imputation model. Baseline characteristics which should be considered in the imputation model include but are not restricted to the baseline values of the respective efficacy variable, the treatment group, and sex.
 2. The imputed data will be modified by applying penalties. The penalty is chosen as the median of the worst changes from baseline across all treatment groups (or 0 if the median worst change should be positive for 6MWD/KCCQ/activity or negative for log-transformed NT-proBNP/hs-TNT).
 3. After modifying the completed data sets, the primary analysis specified in Section 6.2.1.2 will be applied to the multiply imputed datasets and the point estimate and variance of the contrast from multiple imputed dataset will be combined based on Rubin's rule (6). For more details see Appendix 9.4.
- A further sensitivity analysis will be performed where for each patient without an observation at the visit in Week 20 the missing value will be imputed according to a last observation carried forward approach, including the baseline value.

For reproducibility, the SAS seed number for creating the random numbers for the multiple imputation will be set to the study number.

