6.2.2 Secondary efficacy variables and analyses

6.2.2.1 Secondary efficacy variables

Secondary efficacy variables across different domains are:

- AVIVO Activity intensity (weekly average; in %) reported values and absolute change from baseline at 20 weeks
- NT-proBNP (pg/mL), measured values (log transformed) and absolute / relative change from baseline at 20 weeks to assess elevated filling pressures
- High sensitivity troponin T (hs-TNT; ng/L), measured values (log transformed) and absolute / relative change from baseline at 20 weeks as a biomarker of myocardial injury
- Three scores from KCCQ, Physical Limitation, Overall Summary Score and Total Symptom Score (Appendix 9.3), derived values by visit and absolute change from baseline

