6.2.2.3 Sensitivity analyses of secondary efficacy variables

Sensitivity analyses of secondary variables will be performed in the FAS the same way as for primary efficacy variable. If the baseline values of secondary endpoints are missing, then only multiple imputation will be applied for those subjects. Please see the details in Section 6.2.1.4.

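### The secondary MCP-Mod test states no reversed direction for log NT-proBNP and log hs-TNT, so read literally it tests for a rise, which the SAP itself treats as the worst change

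*SAP*

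**What the plan says.** SAP 6.2.2.2 analyses the secondary variables by methods similar to those for the primary variable, which it spells out as "the MCP-Mod method with the same standardized candidate dose-response shapes and corresponding coefficients as for the primary variable". Protocol 10.3.2.3 has the same rule. Neither states a tail for any secondary variable.

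The test that belongs to those coefficients is in SAP 6.2.1.2, Step 1. It sets the null against "the respective 1-sided alternative hypothesis", written there as contrast > 0. With q denoting "the multiplicity adjusted critical value, a dose-response signal is established if" the largest contrast statistic reaches q. Protocol 10.3.2 sets the overall level at one-sided 5%.

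The list in SAP 6.2.2.1 has six variables: activity intensity, NT-proBNP, hs-TNT and three KCCQ scores. The first biomarker is entered as "NT-proBNP (pg/mL), measured values (log transformed) and absolute / relative change from baseline at 20 weeks to assess elevated filling pressures"; hs-TNT is entered in the same form, as a marker of myocardial injury.

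The SAP recognises that these two markers run the other way, but only for missing data:

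- In the worst-value rule for the biomarkers (6.2.2.2), on the worst change per treatment group: "If any of them is negative, the value would be set to 0". For KCCQ and activity the rule zeroes positive values instead.
- In the FAS penalty (6.2.1.4.2, step 2), the median worst change is zeroed if it "should be positive for 6MWD/KCCQ/activity or negative for log-transformed NT-proBNP/hs-TNT".

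Step 3 of that FAS procedure then says "the primary analysis specified in Section 6.2.1.2 will be applied to the multiply imputed datasets", and SAP 6.2.2.3 adds: "Sensitivity analyses of secondary variables will be performed in the FAS the same way as for primary efficacy variable".

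**The concern.** The direction of harm is reversed for imputation and penalty but not for the test that decides whether there is a signal. A programmer who follows the text would run the 6MWD contrasts on the log biomarkers in the upper tail. A dose-related fall would then be reported as no signal, and Step 2 (modelling) would not be reached. A dose-related rise would be reported as a dose-response signal.

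The imputation makes this worse. A patient censored by CV death or HF hospitalization receives a large positive biomarker change. More such patients at the higher doses would push the literal test towards significance.

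Two of the six listed secondary variables are affected. They carry no type I error control (protocol 10.3.2). However, protocol 10.3.2.3 pools primary and secondary evidence to judge the drug effect over doses, and protocol section 4 brings secondary endpoints into the decision on Phase III.

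**Working it through.** **Inputs.** Candidate shapes: SAP Table 6-1. Evaluable patients: 216, as 54/18/36/36/36/36 for 0/5/10/20/30/40 mg (protocol 10.4). Level: one-sided 5%. The documents give no effect size or SD for the biomarkers, so I assume a maximum effect of 0.5, 0.25 or 0.125 SD; 0.5 SD is the protocol's own 40 m / 80 m for 6MWD.

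**Direction of the contrasts.** SAP 6.2.1.2 makes c_i proportional to n_i(mu_i - weighted mean), scaled so that the squares sum to 1. For the linear shape with a maximum of 0.5 SD:

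- Means: 0, 0.0625, 0.125, 0.25, 0.375, 0.5.
- Weighted mean: (18 x 0.0625 + 36 x 1.25) / 216 = 46.125 / 216 = 0.2135.
- n_i(mu_i - mean): -11.53, -2.72, -3.19, 1.31, 5.81, 10.31. The root of the sum of squares is 17.10.
- Placebo weight: -11.53 / 17.10 = -0.674.

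The other placebo weights, obtained the same way, are -0.784 (sigmoid Emax 1), -0.615 (sigmoid Emax 2), -0.901 (Emax) and -0.813 (quadratic). The 20, 30 and 40 mg weights are positive in all five. Every contrast therefore points to a rise over placebo.

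**Reproducing the plan's power.** T_m is the contrast of group means divided by S x sqrt(sum c_i^2 / n_i). The critical value of the maximum, from the five-dimensional t with 216 - 6 = 210 df, is q = 1.968 by simulation (2 million draws).

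| Rise of 0.5 SD, N = 216 | Linear | Sig. Emax 1 | Sig. Emax 2 | Emax | Quadratic |
|---|---|---|---|---|---|
| Protocol Table 10-2 (%) | 80.84 | 91.81 | 87.80 | 88.72 | 86.61 |
| Recomputed (%) | 80.8 | 91.7 | 87.8 | 88.6 | 86.7 |

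So the upper-tail test is the one the protocol powered.

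**The same test on a fall.** Mirror the means and leave the contrasts and tail as written. For the linear shape, the linear contrast statistic is centred near -sqrt(sum n_i(mu_i - mean)^2) = -sqrt(16.945 - 9.850) = -2.66. To reach 1.968 it must move 1.968 + 2.66 = 4.63 standard errors the wrong way. Results for the maximum of the five contrasts:

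| Maximum fall | Test | Linear | Sig. Emax 1 | Sig. Emax 2 | Emax | Quadratic |
|---|---|---|---|---|---|---|
| 0.5 SD | as written (%) | 0.005 | 0.0002 | 0.004 | 0.003 | 0.0005 |
| 0.25 SD | as written (%) | 0.24 | 0.09 | 0.19 | 0.18 | 0.13 |
| 0.25 SD | sign reversed (%) | 34.2 | 44.3 | 39.3 | 40.0 | 39.2 |
| 0.125 SD | as written (%) | 1.23 | 0.85 | 1.09 | 1.07 | 1.00 |
| 0.125 SD | sign reversed (%) | 15.1 | 18.4 | 16.6 | 16.8 | 16.8 |

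At 0.5 SD, reversing the sign restores the figures of the first table, 81-92%. By symmetry the sign-reversed rates are also the rates at which a rise of the same size meets the signal criterion as written. Simulation error affects the last digit only.

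**The case against.** The strongest reply is that the text is silent, not wrong. SAP 6.2.2.2 carries over shapes and coefficients under similar methods; it does not repeat the alternative or the rejection rule. A standardized shape leaves the scale parameter theta_1 free, so a falling response has the same shape with a negative scale. Because the SAP reverses the imputation and penalty for these two markers, any statistician would know which way benefit lies.

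Part of this stands. For the PPS analysis the upper tail is implied, not stated, and the authors very likely meant the beneficial direction. But a free scale parameter does not choose the tail, and the only tail given anywhere is contrast > 0. For the FAS analyses, step 3 and SAP 6.2.2.3 import the 6.2.1.2 test expressly. No section flips the sign.

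Other limits also stand:

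- The percentages show what a one-sided test does in the wrong tail under an assumed effect; they do not show how likely a literal reading is.
- The tests are nominal, and no decision rule rests on their significance.
- A fall would appear in the biomarker summaries and plots (SAP 6.6), in the counts of patients crossing thresholds (SAP 6.2.2.2), and as large negative contrast statistics if those are printed.
- A target-dose threshold is given only for 6MWD, so the loss at the modelling step is small.
- Protocol 9.4.4 labels hs-TNT a marker of baseline disease status only, although both documents list it as a secondary efficacy variable.

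**Conclusion.** The concern holds: a stated procedure, followed exactly, gives the wrong answer for two of six secondary variables. Under the assumed falls, the literal test is significant in at most 0.005% (0.5 SD), 0.09-0.24% (0.25 SD) and 0.85-1.23% (0.125 SD) of trials, always below the 5% it would show with no effect at all. With the sign reversed it is significant in 81-92%, 34-44% and 15-18%.

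These figures rest on 216 evaluable patients in the planned ratio, normal data with equal variance, and the assumed effect sizes. The direction of the error depends only on the contrast signs and the stated tail.

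The 6MWD conclusion, KCCQ and activity are not affected. This should be fixed, since otherwise the specified test may contradict the plots, or the tail may be chosen after unblinding.

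**What to change.** In SAP 6.2.2.2, and for the FAS analyses in 6.2.2.3, add one sentence: for log NT-proBNP and log hs-TNT the contrast coefficients are multiplied by -1 (equivalently, minus the change from baseline is analysed), and H1 is a decrease with dose. If a target dose is estimated for either marker, define it in the same reversed direction. If the team holds no directional hypothesis for hs-TNT, it should say so and specify a two-sided test. KCCQ and activity stay as they are.

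The cost is one sentence in the SAP and a sign in the program. Data collection, sample size and the primary analysis do not change.

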The primary efficacy analysis aims at evaluating the dose-response relationship of the primary and secondary efficacy variables for all randomized patients, who have remained in the study and adhered to study treatment according to the study protocol until Week 20 ("completers and treatment adherers" analysis). Therefore, the primary analysis will be performed in the per protocol set, a subset of the FAS comprising "compliant and adherent" patients (as much as possible, defined via validity criteria). To avoid bias, the PPS will also include those "compliant and adherent" patients who are "censored" due to CV death or a hospitalization for HF preventing the assessment of the relevant efficacy endpoints 20 weeks after randomization, to take place as planned. It is expected, that these are the only patients for

14 FEB 2017 Version: 1.0 Page: 65 of 85

whom missing observations need to be considered in the primary analysis. A "worst case" approach will be used, where the missing change from baseline value will be imputed with a multiple of the worst change from baseline value, which is possible given the individual baseline value observed in the respective treatment group, or 0 if the worst change in that treatment group is positive.

As a sensitivity analysis, a "completers and treatment adherers" only analysis excluding the censored patients in the per protocol analysis set will be performed. This strategy leads to unbiased estimates only if missing values are "missing completely at random" (MCAR), i.e. the missingness – including missing data due to death – is independent of both observed and unobserved outcomes. This condition is unlikely to hold exactly but rather approximately.

Further sensitivity analyses on the PPS may be performed if the missing data patterns suggest further exploration.

Efficacy analysis using the FAS

The efficacy analysis in the FAS aims at evaluating the dose-response relationship of the primary and secondary efficacy variables for all randomized patients. Efficacy analyses in the FAS will include the following:

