6.2.1.2 Primary analysis of primary efficacy variable

The primary efficacy analysis aims at evaluating the dose-response relationship of the primary and secondary efficacy variables for all randomized patients, who have remained in the study and adhered to study treatment according to the study protocol until Week 20 (“completers and treatment adherers” analysis). Therefore, the primary analysis will be performed in the PPS, a subset of the FAS comprising “compliant and adherent” patients (as much as possible, defined via validity criteria). To avoid bias, the PPS will also include those “compliant and adherent” patients who are “censored” due to CV death or a hospitalization for HF preventing the assessment of the relevant efficacy endpoints 20 weeks after randomization, to take place as planned. For missing post-baseline value due to CV death or study drug/study discontinuation due to HF, a worst case approach will be applied. The worst observation value (WOV) would be imputed as follows:

- 1) First, the worst change from baseline value by each treatment group will be calculated. If any of them is positive, the value would be set to 0.
- 2) Secondly the median of the worst changes from baseline value among all treatment groups would be calculated. The change from baseline value for all the missing data will be imputed with a multiplier 1.0 of this median value.
- 3) The WOV (i.e. imputed post-baseline value at week 20) will be calculated accordingly as baseline value + imputed change from baseline. If this imputed WOV for 6MWD is less than 0 (in case of either CV death or a hospitalization for HF preventing the measurement), then the WOV will be replaced with 0 and the imputed change from baseline will be modified to (- baseline value) accordingly.

All other patients with invalid/missing baseline value or missing post-baseline value due to other reasons than the above will be excluded from the PPS.

It is expected, that these are the only patients for whom missing observations need to be considered in the primary analysis. A “worst case” approach will be used, where the missing change from baseline value will be imputed with a multiple of the worst change from baseline value, which is possible given the individual baseline value observed in the respective treatment group, or 0 if the worst change in that treatment group is positive.

Statistical Analysis Plan

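### The worst-case trigger for secondary variables in SAP 6.2.2.2 does not require the HF hospitalisation to have caused the missing Week 20 value, unlike the protocol and the rest of the SAP

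*SAP*

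**What the plan says.** SAP 6.2.2.2 sets the rule for AVIVO activity intensity, log NT-proBNP, log hs-TNT and three KCCQ scores. On the population it states: "The primary analysis of secondary efficacy variables will be performed in PPS". A missing Week 20 value is replaced by the WOV when a baseline value exists and "the subjects have CV death or HF hospitalization, otherwise remain missing".

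The imputed change is not the single worst value in the trial. The worst change is found in each treatment group, and then: "Secondly the median of the worst changes from baseline value among all treatment groups would be calculated". The multiplier is 1.0. For KCCQ and activity, a resulting Week 20 value below zero is set to zero.

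The other statements of the trigger are causal:

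- **Protocol 10.3.3**, for primary and secondary variables in the PPS: CV death or "a hospitalization for HF preventing the assessment of the relevant efficacy endpoints 20 weeks after randomization".
- **SAP 6.2.1.2**, for 6MWD: "For missing post-baseline value due to CV death or study drug/study discontinuation due to HF, a worst case approach will be applied". This section and 6.2.1.4.1 also repeat the protocol's condition.
- **SAP 6.2.1.4.2**, for the full analysis set (FAS), which 6.2.2.3 extends to secondary variables: the value must be missing because of CV death or an HF hospitalisation before the Week 20 visit.

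Within 6.2.2.2, causal wording occurs once, in the parenthesis of the floor-at-zero step for KCCQ and activity: "in case of either CV death or a hospitalization for HF preventing the measurement". The biomarker steps have none.

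**The concern.** A worst-case value is justified when the missing measurement itself reflects a bad clinical outcome. The operative sentence in 6.2.2.2 drops that link. A patient admitted for HF at Week 3 who recovers, attends Week 20 and completes the walk test, but whose activity sensor failed or whose troponin sample was lost, meets the trigger. Because no time window is given and events are followed to Week 26 (Protocol 9.2.10, SAP 6.2.3), an admission after Week 20 also meets it.

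The plan shows how such gaps can arise. Patients apply the Week 20 activity sensor themselves at Week 19, and Protocol 11.4 lists measures against loss of sensor data. The KCCQ Physical Limitation score is missing when fewer than three of its six items can be scored, and items limited for other reasons, or not done, are coded as missing (SAP 9.3.1).

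What is at stake is the reading of the secondary variables. Protocol 10.3.2.3 combines them with the primary variable as the totality of evidence, and Protocol section 4 brings them into the Phase III decision. The PPS and FAS results would also differ in imputation trigger as well as population, which makes them harder to compare.

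**Working it through.** **1. The passages side by side.**

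| Place | Variables | Event must cause the missing value? | Time limit? |
|---|---|---|---|
| Protocol 10.3.3 (PPS) | primary and secondary | yes | tied to the Week 20 assessment |
| SAP 6.2.1.2 | primary rule; aim stated for both | yes | tied to Week 20 |
| SAP 6.2.1.4.1 | aim stated for both | yes | tied to Week 20 |
| SAP 6.2.1.4.2 with 6.2.2.3 (FAS) | both | yes | before the Week 20 visit |
| SAP 6.2.2.2, operative sentence | secondary | no | none |
| SAP 6.2.2.2, floor step | KCCQ and activity | yes, in a parenthesis | none |
| SAP 6.2.2.2, biomarker steps | NT-proBNP, hs-TNT | no | none |

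**2. Can the rule reach anyone in the PPS?** SAP 6.2.1.2 removes from the PPS patients whose value is missing for other reasons, but it is written for 6MWD. A patient with a valid Week 20 6MWD can stay in the PPS and still lack activity, a KCCQ score or a biomarker. The closing words of "the subjects have CV death or HF hospitalization, otherwise remain missing" show that the SAP expects missing secondary values inside the PPS.

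**3. Base.** The plan gives no figure for this rule. Its own PPS estimate is 288 x 0.75 = 216, which at 3:1:2:2:2:2 is 54 on placebo, 18 on 5 mg and 36 in each other dose group.

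**4. Number affected.** Neither rate below is in the documents; both are assumptions, taken as independent.

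Patients = 216 x (share with HF hospitalisation) x (share with unrelated missing activity data)

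- Central: 216 x 0.05 x 0.20 = 2.2
- Low: 216 x 0.03 x 0.10 = 0.6
- High: 216 x 0.08 x 0.30 = 5.2

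These figures are for activity only. No rate is assumed for KCCQ or the biomarkers.

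**5. Size of the WOV.** With normally distributed changes, equal means and the group sizes in step 3, simulation (40,000 runs) puts the median of the six group-worst changes at -2.07 SD on average (5th to 95th percentile -2.45 to -1.73). For biomarkers the sign is reversed. For KCCQ and activity, the floor at zero makes it smaller in patients with low baseline values.

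**6. Shift in a group mean per affected patient** = WOV / n, with the patient counted in n.

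- n = 18: -2.07 / 18 = -0.115, about -0.12 SD
- n = 36: -2.07 / 36 = -0.058, about -0.06 SD
- n = 54: -2.07 / 54 = -0.038, about -0.04 SD

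**7. Balanced and unbalanced cases.**

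- Spread evenly, 2.2 patients in 216 is 2.2 x 36 / 216 = 0.36 per 36-patient arm, or about 0.36 x 0.058 = 0.02 SD. The expected shift is similar in every arm and largely cancels in the contrasts.
- If all fall in one 36-patient dose arm with a true difference of 0.5 SD (the planning effect for 6MWD, borrowed as an illustration), the observed difference is 0.5 x (36 - x)/36 - 2.07x/36. That gives 0.43, 0.36 and 0.29 SD for x = 1, 2 and 3.

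**The case against.** The best defence is that the sentence in 6.2.2.2 is shorthand. The section says secondary variables are analysed by methods similar to the primary, its floor step speaks of hospitalisation preventing the measurement, and neighbouring SAP sections state the causal condition for both sets of variables. This makes a causal intention likely. It does not settle what will be programmed: the parenthesis qualifies only the flooring of negative values, it does not define who is imputed, and the biomarker steps have nothing like it.

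A second defence is that an event-based trigger is more objective. HF hospitalisations are adjudicated by the Clinical Events Committee, while no process is described for judging whether one prevented a measurement. That is a fair practical point, but the plan does not make it, and the protocol and the rest of the SAP use the causal form.

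Third, the damage is contained. Through 6.2.2.3, secondary variables also get FAS analyses, one of them without imputation, and Protocol 10.3.2 gives them no type I error control. This stands, and it is why the point is minor.

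A reader might infer more than the documents support:

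- **That the SAP deliberately replaced the protocol's rule.** SAP section 7 lists only approval dates, and the SAP repeats the causal condition elsewhere.
- **That any randomised patient with an HF admission is given the worst value seen.** The rule needs PPS membership, an available baseline and a missing Week 20 value, and the imputed change is a median of group-worst changes.
- **That device failure is known to be common here.** Neither document gives a rate.

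**Conclusion.** The inconsistency is real. As written, the trigger for secondary variables in the PPS is wider than the one in the protocol and in three other SAP sections, and it can score a technical gap as a change of about 2 SD in the unfavourable direction. This is a stated rule that gives a wrong result in identifiable cases, not merely missing detail.

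The consequence is probably small: about 2 of 216 PPS patients for activity (0.6-5), on assumed rates and independence. The size per patient also assumes normal changes and the planned group sizes. Bias in the dose-response contrasts needs an imbalance between arms, and the 18-patient 5 mg arm is the most sensitive. The point concerns secondary variables only.

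**What to change.** In SAP 6.2.2.2, replace the trigger for all secondary variables, biomarkers included, with wording such as: *if the baseline value is available and the Week 20 value is missing because of CV death or an HF hospitalisation that occurred before the Week 20 visit and prevented the assessment; any other missing value stays missing.*

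Two related points should be settled in the same edit:

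- Align this wording with SAP 6.2.1.2, whose trigger refers to study drug or study discontinuation due to HF, so that primary and secondary variables share one definition.
- Keep the statement that other missing secondary values stay missing. Protocol 10.3.3 does not address them; it expects no other missing observations in the PPS.

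To keep the rule objective, the blind review could record for each affected patient whether the hospitalisation prevented the assessment. The cost is a short wording change in the SAP and a matching change in the imputation program, with no new data collection and no effect on sample size.
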